Specifically, we propose to evaluate mechanism effects of the three treatments using a 3-wave SEM approach⁹⁸⁻¹⁰². To address Aim 1, we will calculate coefficients representing the linear change in each outcome and mechanism variable during the first two weeks of treatment (early treatment) and second two weeks of treatment (late treatment). To accomplish this, the slope of the regression line for predicting scores from the time variable will be obtained, where the Time variable consists of equally spaced fractions from 0 to 1 for each epoch (i.e., early treatment and late treatment represent two time epochs). While the majority of participants will provide many data points during these time periods, we only need two (representing just 2/24 EMA assessments, or 8% of requested data) ratings in each time period to be able to calculate the slopes for the planned analyses (see below for how any data deemed to be missing at random will be handled using this slope method). To address Aim 1, the time epochs/slopes will be operationalized/calculated as described below:

1. Pre-treatment scores: Slope calculated from EMA ratings/ActiGraph data from all available baseline data (i.e., from days 1-14, see Figure 2).
2. Early-treatment scores: Slope calculated from EMA ratings/ActiGraph data from the first day following the baseline period to mid-treatment (i.e., days 15-28, see Figure 2).
3. Late-treatment scores: Slope calculated from EMA ratings/ActiGraph data from the first day following the mid-treatment mark until the last day of the treatment period (i.e., days 29-42, see Figure 2).

To address the secondary Aim 2, we will calculate slopes from EMA and ActiGraph data across two time periods to compute scores for early and late post-treatment change for the primary outcome (pain interference) and the three mechanism variables (catastrophizing, non-judgment, and activity level), as operationalized below:

1. Early post-treatment scores: Slope calculated from EMA ratings/ActiGraph data from the first day following treatment until 2-weeks following treatment (i.e., from days 43-56, see Figure 2).
2. Late post-treatment scores: Slope calculated from EMA ratings/ActiGraph data from the first day following mid-post-treatment follow-up epoch until the end of the 4-week post-treatment period (i.e., days 57-70, see Figure 2).

Figure 2. EMA data collection and data time points used in analyses

[figure not shown]
[figure not shown]

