Because it is likely that we will encounter at least some missing data despite procedural efforts by research staff to minimize its occurrence, we have attempted to further address missing data in a number of ways via our data analysis approach. First, we will examine potential patterns of missing data that represent confounds contributing to biased slopes. So, for each participant, analyses to identify potential patterns in missing data will be conducted to determine if they are “ignorable” (see Schafer & Grahem, 2002)¹⁰⁷. If >5% of the participants do not provide adequate data, the sample will be divided into two groups (missing data, no missing data) and fully observed variables will be examined to determine if they significantly predict missingness on the affected outcome. This test will be done on a variable-by-variable basis. If this analysis is non-significant, the missingness will be considered “observed at random” and the procedures described below for calculation of slope coefficients in the instance of missing data will be used, without necessitating the use of multiple imputation procedures. However, if no data is available to calculate slope via the below methods, in Mplus, the missing data (slopes and estimated end values from slopes) are treated automatically (by default) by estimating the full model from available data using full information maximum likelihood (FIML). The Mplus robust maximum likelihood (MLR) estimator using FIML permits missing completely at random (MCAR) and missing at random (MAR), and MLR uses SEs that are corrected for non-normality and also uses a corrected chi-square fit statistic. If data missingness is not ignorable, Heckman’s selectivity models of pattern-mixture models with multiple imputation will be used to model the “missingness” for each participant before calculation of slopes from the daily EMA and ActiGraph data.

There are several ways to treat data that are deemed to be missing at random (from the daily EMA and ActiGraph data) using the slope method. For example, consider the six cases below (from real data). The dependent variable was measured at five equally spaced intervals within the epoch. Within the current study, there are additionally two observations per day, and we propose to calculate the slopes from morning and evening observations, and to average those slopes.

Cases	0	0.25	0.5	0.75	1	Slope	Difference
1	12	14	15	15	10	-1.2	-2
2	12	10	11	10	7	-4	-5
3	23	19	13	13	12	-11.2	-11

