4	15	16	12	13	8	-6.8	-7
5	29	21				-32	
6	21	22	15	20	12	-8	-9

In the above example, for Case 5, the slope is estimated to be -32, because it is based on the first two Time points, where there is a substantial decline. The decline is magnified by extrapolating the line over the full time period, and the score is probably an outlier. Hence, there are weaknesses to the slope method. However, one approach is to carry the last observation forward and first observation backward when there are missing data at the beginning or end of an epoch. The difference for Case 5 would then be -8 and the slope would be -6.15. Given there are four epochs in the current study, this method becomes somewhat complicated. However, we propose to carry forward or carry backward the closest score in the full sequence of scores from the beginning of pre-test to the end of post-test.

D6u. Power Analyses

We will conduct **six primary** statistical tests to test the primary aim for three mechanism variables, in order to better understand the effects of the treatments on pain interference. Data from prior research – including means and standard deviations – was used to support the anticipated medium to strong effects of the mechanism paths that we propose to test, and which form the basis of our assumptions for the power analyses.

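### Slopes estimated from the diaries enter the SEM as if measured without error and with equal weight; the carry rule removes extreme values but not the likely attenuation of b for the two diary mechanisms.

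*Combined protocol and SAP*

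**What the plan says.** D6s (Statistical Analyses) defines the scores: for each participant and epoch, "the slope of the regression line for predicting scores from the time variable will be obtained", with time running from 0 to 1. The early-treatment epoch runs "from the first day following the baseline period to mid-treatment (i.e., days 15-28, see Figure 2"; late treatment is days 29-42. On sparse diaries D6s says "we only need two (representing just 2/24 EMA assessments, or 8% of requested data) ratings in each time period".

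D6t (Missing Data) adds that "we propose to calculate the slopes from morning and evening observations, and to average those slopes". It makes clear that the slopes are the analysis variables: where none can be computed, "the missing data (slopes and estimated end values from slopes) are treated automatically (by default") by FIML. On the estimator it says "MLR uses SEs that are corrected for non-normality and also uses a corrected chi-square fit statistic".

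D6t also shows a weakness of the method. In its six-case example, Case 5 has two ratings and a slope of -32, and the text comments: "The decline is magnified by extrapolating the line over the full time period, and the score is probably an outlier". The remedy follows in the same paragraph: "we propose to carry forward or carry backward the closest score in the full sequence of scores".

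Neither section mentions a latent slope, a reliability correction or a precision weight. D6s takes a non-significant b as lack of support for that mechanism. D6u (Power Analyses, Table 5) uses r = 0.30 for paths a and b and has no entry for slope reliability.

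**The concern.** This is a two-stage analysis. Stage one estimates a slope for each person; stage two analyses those estimates as if they were the true slopes. Two consequences follow.

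First, an early mechanism slope is the true slope plus sampling error. When it is the predictor in path b, independent error shrinks b toward zero. Robust standard errors do not correct this, because it is bias in the coefficient and not non-normality.

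Second, precision differs greatly between people, yet each slope counts once. The unweighted morning/evening average repeats the problem within a person: the sparser series gets half the weight.

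At stake is the reading of the primary mechanism tests. A noisy slope makes a null b more likely, and the plan gives a null b a substantive interpretation. If slope reliability differs between mechanisms, that difference could also pass for a difference in their importance.

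**Working it through.** **The plan's own figures.** Least squares reproduces all six slopes in the D6t table (-1.2, -4, -11.2, -6.8, -32, -8). Table 5 gives n = 109 / 129 / 140 for the mediation rows at alpha .050 / .025 / .017. Requiring power(a) × power(b) ≥ .80 at r = .30, two-sided, gives 111 / 131 / 142 with Fisher's z and 107 / 126 / 137 with the non-central t. Table 5 therefore stands on its assumptions.

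**Case 5 under the carry rule.** The filled series is 29, 21, 21, 21, 21. Sxy = -0.5×29 - 0.25×21 + 0.25×21 + 0.5×21 = -4 and Sxx = 0.625, so the slope is -6.4 (D6t prints -6.15). The five complete cases average (-1.2 - 4 - 11.2 - 6.8 - 8)/5 = -6.24. The rule brings this case into line.

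**Precision of a slope.** Let σ be the within-person residual SD.
- Full epoch, 14 days: Sxx per series = 14×15/(12×13) = 1.346. SE of the averaged morning/evening slope = σ√(1/(2×1.346)) = 0.61σ.
- Two adjacent days in one series, no carry: Sxx = (1/13)²/2 = 0.00296, so SE = 18.4σ. The variance ratio is 338/0.371 = 910.
- Random subsets of 14, 7 and 4 ratings, one line without carry: variance about 2.2, 5.4 and 16 times that with 28 ratings.

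(Twice-daily ratings over 14 days make 28, so two ratings are 2/28 = 7%, not the stated 2/24.)

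**Reliability.** With k = SD(true slope)/σ, reliability on full data = k²/(k² + 0.371). The documents do not give k, so a range is assumed:

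| k | 0.5 | 0.75 | 1 | 1.5 | 2 |
|---|---|---|---|---|---|
| Reliability | .40 | .60 | .73 | .86 | .92 |

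**Attenuation and power for b.** Take .30 as the error-free correlation, with equal reliability for mechanism and outcome slopes, so observed r = .30 × reliability. Power = Φ(√237 × atanh(r) - z), N = 240:

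| Reliability | .9 | .8 | .7 | .6 | .5 | .4 |
|---|---|---|---|---|---|---|
| Observed r | .27 | .24 | .21 | .18 | .15 | .12 |
| Power, alpha .05 | 99% | 97% | 91% | 80% | 64% | 46% |
| Power, alpha .017 | 97% | 92% | 82% | 66% | 48% | 30% |

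Power for b stays at 80% down to reliability of about .60 (alpha .05) or .69 (alpha .017). For the joint test of a and b the limits are about .63 and .72.

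**Does the carry rule remove the attenuation?** Simulated with true r = .30, N = 240, independent errors and 80% of ratings present; in the last two rows 10% of participants have only the first 2-4 days of an epoch:

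| k | 0.5 | 1 | 2 |
|---|---|---|---|
| No sparse diaries, observed r | .09 | .19 | .27 |
| 10% sparse, no carry | about .00 | .04 | .12 |
| 10% sparse, carry | .09 | .19 | .25 |

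Carrying undoes most or all of the damage from sparse diaries. It leaves the attenuation that was present without them. (The simulation carried within an epoch; the plan carries over the full sequence.)

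**Does correction help?** In a further simulation (carry rule, true b = .30, independent errors, assumed completion), b was .26 / .22 / .18 / .13 with residual SD .5 / .75 / 1 / 1.5 times the true slope SD. An error-corrected, precision-weighted version recovered about .30. Power was 78-98% for the current method against 83-98% at ratios up to 1, and 53% against 65% at 1.5.

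**The case against.** The best defence is that the plan has seen the sparse-diary problem and answered it. A reader might infer from the -32 in D6t that such values will enter the primary model. The documents do not support that: the same paragraph proposes the carry rule, and the check shows that it works on extremes. What remains is that the rule is worded tentatively, counts filled values as observed, and does not address attenuation.

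A reader might also infer that all three b tests suffer from missed diaries. They do not. The activity mechanism is ActiGraph counts from a device worn all day, so survey completion affects that model only through the pain-interference slope. Noise in an outcome lowers power without biasing the unstandardised b. Day-to-day noise in the activity slope could attenuate b, but its size is not given.

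Nor can it be said that r = .30 is wrong or the trial underpowered. D6u uses .30 as a medium benchmark and supports it with observed, already error-containing associations (0.57; -0.30 and -0.35). The planned 240 is well above Table 5's 109-140. Completion may also be good: Section C reports 86% and 88% in earlier diary studies, and F4d calls for discussion below 80%. What stands is narrower: none of the cited associations is between an early and a later two-week slope, and no reliability is stated.

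Finally, bias toward zero is likely but not certain. Mechanism and outcome come from the same diary, so their errors may correlate, and the full path set of Figure 3 is not available here. With independent errors, attenuation does not inflate false positives.

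**Conclusion.** The point holds in a limited form. The plan uses estimated slopes as error-free, equally weighted data, and its carry rule cures the outliers but not the attenuation. For catastrophizing and non-judgment, b is likely too small if errors are independent. For activity, the documents establish only a loss of precision through the outcome slope.

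The size depends on slope reliability, which is unknown. At .8 or above, power for b at N = 240 remains at least 92% at alpha .017, and the main harm is an understated coefficient. Below about .60-.69, power for b falls under 80% and a null result becomes hard to read as lack of support. These thresholds assume equal reliabilities and an error-free correlation of .30, which the plan does not claim. The change is worth making because it is cheap and bears on how the primary tests are interpreted; it is not a finding that the trial is too small.

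**What to change.** 1. Estimate epoch-specific random slopes inside the model from the raw ratings, as a multilevel or latent growth SEM in Mplus with a morning/evening term, and place a and b among the latent slopes. Sparse diaries then contribute according to their information, without filled values.
2. If that does not converge, fit one pooled regression per participant and epoch with a morning/evening term, and error-correct and weight each slope by its sampling variance. Pooling without weighting is not enough.
3. Report slope reliability for each mechanism and for pain interference, and show power over a range of attenuated r beside Table 5.
4. Keep the current carry-forward slopes as a sensitivity analysis.

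No new data, participants or software are needed. The cost is more programming and possible convergence problems, for which step 2 is the fallback.

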For all participants who are randomized to receive one of the three study treatments but are unable to participate in that cohort's treatment sessions, the participant will always be asked to complete study assessments for that cohort and included in study analysis unless they withdraw their participation from the study. This means that, post-randomization, if a participant is unable to attend the treatment s/he was assigned to OR decides to withdraw from treatment, s/he will be offered the opportunity to continue with EMAs, wear the activity monitor, and complete extended assessments for that cohort in which randomization had occurred. The participant will not be allowed to defer to another cohort to participate in treatment. Once a participant is randomized, s/he cannot be deferred to a later treatment cohort, even if they do not participate in a single session of the cohort they are randomized in. If a participant needs to defer to another cohort, this is only allowed **before** they have been randomized.

D6n. Study Design Enhancements: Treatment Fidelity, Missed Sessions and EMA Assessments, Participant Engagement, and Study Retention Strategies

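### Filling epoch-edge gaps with the closest score flattens the slopes of participants who stop reporting; the bias is modest, but the rule, its trigger and the handling of empty epochs need rewording

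*Combined protocol and SAP*

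**What the plan says.** D6s makes the early-treatment slope (days 15-28) and the late-treatment slope (days 29-42) the variables of the Aim 1 structural equation model. On the data needed for a slope it says "we only need two (representing just 2/24 EMA assessments, or 8% of requested data) ratings in each time period".

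D6t gives the missing-data rules in this order:

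- If more than 5% of participants lack adequate data, observed variables are tested as predictors of missingness. "If this analysis is non-significant, the missingness will be considered" observed at random, and the slope procedures are used without multiple imputation.
- FIML is used "if no data is available to calculate slope via the below methods". D6t adds that the Mplus estimator "permits missing completely at random (MCAR) and missing at random (MAR").
- If missingness is judged not ignorable, selection or pattern-mixture models with multiple imputation come before the slopes are calculated.
- On twice-daily ratings: "we propose to calculate the slopes from morning and evening observations, and to average those slopes".
- To contain extreme slopes, D6t suggests one may "carry the last observation forward and first observation backward when there are missing data at the beginning or end of an epoch". It illustrates this with Case 5, whose slope moves from -32 to -6.15. For this trial it then extends the idea: "we propose to carry forward or carry backward the closest score in the full sequence of scores", running from pre-test to post-test.

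**The concern.** A carried score enters the slope as if it had been observed. FIML and robust standard errors act on missing slopes, so they cannot undo a slope that the carry has already flattened. The people affected are those who stop reporting while still improving or worsening.

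Three gaps in the wording add to this:

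- The text does not say whether carried scores count toward the two-rating minimum. That minimum is stated per epoch, although slopes are fitted per morning and evening stream.
- The text does not exclude filling both ends of an empty epoch with the same earlier score, which gives a slope of exactly 0.
- The method is chosen by a significance test that cannot do that job. A non-significant result does not establish ignorability. A significant one shows that observed variables predict missingness, which is compatible with MAR, the condition that D6t says FIML permits.

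At stake are the mean early and late changes (the average early slope also feeds the Step 1 screen in D6s) and, on the slope-0 reading, the b tests.

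**Working it through.** **1. The plan's own example.** The least-squares slope is Σ(t - t̄)(y - ȳ) / Σ(t - t̄)². For Case 5, carry the last score to the end point only: t = 0, 0.25, 1 and y = 29, 21, 21. Then t̄ = 0.4167 and ȳ = 23.667. The numerator is -2.222 + 0.444 - 1.556 = -3.333 and the denominator is 0.1736 + 0.0278 + 0.3403 = 0.5417. The slope is -6.154, which matches -6.15. Filling all three gaps gives -6.40, so the example fills only the end point, although the text does not say so. The observed-only slope of -32 is not the truth either, and D6t itself calls it a probable outlier. The example shows the direction of the effect, not the size of the bias.

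**2. One participant.** Assume straight-line change over 14 days with one noise-free value per day, observed through day k, and the last value placed at t = 1. The share of the true slope kept for k = 1 to 13 is 0, .045, .100, .170, .256, .357, .470, .585, .695, .791, .870, .929, .971 (sum 6.239). Stopping after day 4, 7 or 10 thus keeps 17%, 47% or 79%.

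**3. The whole sample.** Let a share p stop, with the last observed treatment day uniform on 0 to 27. This pattern is assumed. D5 plans for 20% dropout, but from enrolment to complete data, so p = 20% is an upper scenario.

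- Early, empty epochs missing: [1 - p + 14p/28 + 6.239p/28] / (1 - p/28). At p = .20: (.800 + .100 + .0446) / .9929 = .951.
- Late, empty epochs missing: [1 - p + 6.239p/28] / (1 - 15p/28). At p = .20: .8446 / .8929 = .946. The share with an empty late epoch is 15(.20)/28 = .107.
- Late, empty epochs scored 0: the numerator alone, .845.

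| p | Early kept | Late kept | Late kept, empty = 0 |
|---|---|---|---|
| 20% | .951 | .946 | .845 |
| 10% | .976 | .974 | .922 |
| 5% | .988 | .988 | .961 |

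**4. The tests.** An illustrative simulation used N = 300, 150 runs per setting, slope SD 1, residual SD 1, daily autocorrelation .3, mechanism-outcome residual correlation .6, and 14% scattered gaps (from the 86% diary adherence in section C). Complete cases stood in for FIML. With 20% stopping and true b = .30 (true mean changes 1):

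| Rule | Mean early | Mean late | b | Power for b |
|---|---|---|---|---|
| Carry, empty missing | .958 | .949 | .157 | 75% |
| Carry confined to the epoch | .951 | .939 | .160 | |
| Observed only, minimum 2 | 1.007 | 1.002 | .164 | 49% |
| Observed only, minimum 5 per stream | 1.011 | .999 | .168 | 74% |
| Carry, empty = 0 | .950 | .847 | .171 | |
| Random slopes | 1.009 | .999 | .277 | |

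- With complete data, two-stage slopes give b = .181 and random slopes .284.
- With scattered gaps and no stopping, the carry gives b = .163 against .164 from observed ratings.
- With true b = 0 and empty epochs missing, rejection is 6.7% (mean change 1 slope SD) and 3.3% (2 SD). The Monte Carlo SE is about 2 points.
- With empty epochs scored 0, rejection is 5.3% and 32.7% (23.3% after adjusting for the early outcome slope).
- A separate run (80 per arm, 300 runs) with unequal stopping of 10/20/30% by arm left the a test at 5-7%.

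**5. The 2/24 figure.** Epochs of 14 days with two ratings a day hold 28 ratings, so two ratings are 2/28 = 7%, not 8%. D6j, however, runs the treatment period from the day of Session 1 to the day of Session 8. If the two weekly sessions were two days apart, that would be 24 days, 48 surveys and 24 per half. The two passages conflict; the documents do not show which is wrong.

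**The case against.** The carry has a stated purpose, and the simulation supports it. Deleting it while keeping a two-rating minimum brings back unstable slopes and cuts power for b from 75% to 49%. On the natural reading, b, its power and its type I error under the carry are within noise of observed-only slopes with a minimum of five (power 75% against 74%, SE about 3.5 points). Mean change is not one of the six primary tests. The plan also limits how often people stop: someone who leaves treatment is told that "s/he will be offered the opportunity to continue with EMAs", and there are a 7/14 run-in, daily monitoring, payment and an 80% adherence trigger. Data judged non-ignorable are imputed before slopes are formed. All of this stands. It bears on how often the problem occurs and on its effect on the tests, not on what the carry does to a slope once reporting stops.

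A reader might infer four stronger things, which are not supported:

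- **That the carry invalidates the b tests.** The large distortions need empty epochs scored 0. The carry is described for gaps at the ends of an epoch, which presupposes ratings inside it, and scoring every empty epoch 0 would leave the FIML clause almost nothing to do.
- **That borrowing across epochs is the harm.** Confining the carry to the epoch keeps slightly less of mean change (.951/.939 against .958/.949).
- **That the gap between .16 and .28 measures the carry.** Most of it is slope measurement error that two-stage slopes have with complete data (.18). The random-slope fit also took the residual covariance as known, an advantage a real analysis lacks.
- **That 2/24 is simply an error.** See step 5.

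**Conclusion.** The point holds in a limited form. The carry biases mean early and late change toward zero: about 5% if 20% of participants stop evenly over treatment, 2-3% at 10% and 1% at 5%. The effect on the a and b tests is small. Only the slope-0 reading of an empty epoch raises the loss to about 16% of mean late change at 20% stopping; false rejection of b = 0 then reaches 33% if mean change is 2 slope SD, but stays at 5% at 1 SD. One sentence can exclude that reading. The significance-test trigger is wrong as written, whatever the amount of missing data.

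Step 3 rests on straight-line change and uniform stopping. Step 4 rests on variances and correlations that the documents do not give, and on complete cases in place of FIML. Neither describes the ActiGraph mechanism, which is not a twice-daily survey stream. This is worth correcting before analysis; it is not grounds for doubting the primary tests.

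**What to change.** Reword D6t and the matching text in D6s:

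- Drop the carry from the primary analysis. Compute each slope only from ratings observed within its epoch.
- Prespecify a minimum count above two for each of the morning and evening streams, for example five, and state a separate minimum for ActiGraph data.
- Treat an epoch below the minimum, including an empty one, as missing under FIML, never as slope 0.
- Do not let the test of missingness predictors choose the method. Report it descriptively and run the pattern-mixture analysis as a sensitivity analysis in any case.
- Reconcile 2/24 (8%) with the 14-day, twice-daily epochs, which give 2/28 (7%).

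A latent growth or random-slope model in Mplus is an acceptable alternative. If it is chosen, its larger gain in b should be credited mainly to removing slope measurement error.

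The cost is SAP wording and some programming in software already named; no new data are needed. With 20% stopping and a minimum of five per stream, usable early slopes fall from 99% to 96% and late slopes from 89% to 86%, with power for b essentially unchanged.
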